3.5.2 Safety Outcome Measures

The safety outcome measures for this study are as follows:

- Incidence, nature, and severity of adverse events, graded according to the NCI CTCAE v4.0
- Changes in vital signs, physical findings, and clinical laboratory results

A Data Monitoring Committee (DMC) will be used to evaluate safety during the study. Safety data will be reviewed by the DMC on a periodic basis, approximately every 3 months from the date of first-patient-in. In addition, the DMC will review safety data 28 days after the inclusion of the 6th patient. Safety data, including demographics, adverse events, serious adverse events, and relevant laboratory data, will be reviewed.

The DMC will provide a recommendation as to whether the study may continue, whether amendment(s) to the protocol should be implemented, or whether the study should be stopped. The final decision will rest withthe Sponsor.

3.5.3 Patient-Reported Outcome Measures

The PRO outcome measures for this study are as follows:

- EORTC QLQ-C30
- EORTC QLQ-CR29
- EuroQol EQ-5D

3.5.4 Exploratory Outcome Measures

The exploratory outcome measures for this study are as follows:

Longitudinal plasma samples (liquid biopsy and PBMCs) will be collected at baseline and every 4-week until best response according to ir-RECIST; after that, these samples (liquid biopsy and PBMCs) will be collected every 8 +/-1 weeks for the first 12 months and every 12 weeks thereafter and at disease progressionleading to treatment discontinuation. Patients will undergo an optional tumor biopsy sample collection, if

clinically feasible as assessed by investigators prior to C3D1 of the second treatment phase and/or at the evidence of radiographic disease progression causing treatment discontinuation. A separate informed consent will be signed for optional biopsies requested by the study.

Quantification of the percentage of MGMT methylation (by digital PCR based methods, i.e. methyl-BEAMing) and MGMT IHC will be performed in archival tumor tissue and tumor re-biopsies. Digital PCR for MGMT methylation status will be performed in cell-free circulating DNA (cfDNA) (cfDNA). Mutational load will be assessed in archival tumor tissues, tumor biopsies and cfDNA by means of whole exome sequencing. Immune-related tissue and circulating biomarkers will also be studied.

3.6 Post Study Access to Therapy

At the conclusion of the study, subjects who continue to demonstrate clinical benefit will be eligible to receive study drug. Study drug will be provided via an extension of the study, a rollover study requiring approval by responsible health authority and ethics committee or through another mechanism at the discretion of the Sponsor. The Sponsor reserves the right to terminate access to study drug if any of the following occur: a) the marketing application is rejected by responsible health authority; b) the study is terminated due to safety concerns; c) the subject can obtain medication from a government sponsored or private health program; or d) therapeutic alternatives become available in the local market.

4 STUDY POPULATION

The study is expected to screen approximately 400 patients to enroll approximately 100 patients who meet the eligibility criteria in the first lead-in treatment phase and 27 patients in the combination treatment phase.

4.1 Inclusion Criteria

Patients must meet the following criteria for study entry:

- 1. Have provided written informed consent prior to any study specific procedures
- 2. Willing and able to comply with the protocol.
- 3. \geq 18 years of age.
- 4. ECOG status 0 1.
- 5. At least 12 weeks of life expectancy at time of entry into the study.
- 6. Histologically confirmed metastatic or inoperable adenocarcinoma of the colon and/or rectum, with centrally confirmed mismatch repair proficiency (microsatellite stable [MSS]) by multiplex polymerase chain reaction (PCR), MGMT promoter methylation by pyrosequencing and MGMT absent expression by IHC.
- 7. Patients with progressive disease or that are not candidate for oxaliplatin irinotecan fluoropyrimidine based chemotherapy and anti EGFR mAbs (in RAS/BRAF wild type tumors) in the metastatic setting.
- 8. Patients with documented disease relapsed within 6 months from the completion of adjuvant oxaliplatin-based chemotherapy are considered eligible.
- 9. Measurable, unresectable disease according to RECIST 1.1. Subjects with lesions in a previously irradiated field as the sole site of measurable disease will be permitted to enroll provided the lesion(s) have demonstrated clear progression and can be measured accurately.
- 10. Is willing and able to provide an adequate archival tumor sample (FFPE) available for tissuescreening for central tissue screening. If the tumor block is not available, a minimum of twentyfive 3-micron unstained sections on charged slides of tumor will be required.

4.2 Exclusion Criteria

Patients who meet any of the following criteria will be excluded from study entry:

- 1. Requirement for treatment with any medicinal product that contraindicates the use of any of the study medications, may interfere with the planned treatment, affects patient compliance or puts the patient at high risk for treatment-related complications.
- 2. Inability to swallow pills.
- 3. Refractory nausea and vomiting, malabsorption, external biliary shunt or significant bowel resection that would preclude adequate absorption.
- 4. Inadequate hematological function indicated by all of the following:
 - White Blood Cell (WBC) count $\leq 2 \times 10^9/L$
 - Absolute neutrophil count (ANC) $< 1.5 \times 10^9/L$
 - Platelet count $< 100 \times 10^9/L$
 - Hemoglobin < 9 g/dL (patients may have transfusions and/or growth factors to attain adequate Hb)
- 5. Inadequate liver function indicated by all of the following:
 - Total bilirubin ≥ 1.5 x upper limit of normal (ULN)
 - Aspartate transaminase (AST) and alanine aminotransferase (ALT) \geq 3 x ULN (\geq 5 x ULN in patients with known liver metastases)
 - Alkaline phosphatase (ALP) ≥ 2 x ULN (≥ 5 x ULN in patients with known liver metastases)
- 6. Inadequate renal function indicated by all of the following:
 - Serum creatinine > 1.5 x ULN or calculated creatinine clearance < 40 ml/min
- 7. INR > 1.5 and aPTT > 1.5 x ULN within 7 days prior to the start of study treatment for patients not receiving anti-coagulation.
 - a. NOTE: The use of full-dose oral or parenteral anticoagulants is permitted as long as the INR or aPTT is within therapeutic limits (according to the medical standard of the enrolling institution) and the patient has been on a stable dose of anticoagulants for at least two weeks prior to the start of study treatment
- 8. Active infection requiring intravenous antibiotics at the start of study treatment.
- 9. Previous or concurrent malignancy, except for adequately treated basal or squamous cell skin cancer, superficial bladder cancer, or carcinoma *in situ* of the prostate, cervix, or breast, or other cancer for which the patient has been disease-free for three years prior to study entry.
- 10. Evidence of any other disease, neurologic or metabolic dysfunction, physical examination finding or laboratory finding giving reasonable suspicion of a disease or condition that contraindicates the use of any of the study medications, puts the patient at higher risk for treatment-related complications or may affect the interpretation of study results.
- 11. Clinically significant (i.e. active) cardiovascular disease, for example cerebrovascular accidents ≤ 6 months prior to start of study treatment, myocardial infarction ≤ 6 months prior to study enrolment, unstable angina, New York Heart Association (NYHA) Functional Classification Grade II or greater congestive heart failure, or serious cardiac arrhythmia uncontrolled by medication or potentially interfering with protocol treatment.
- 12. History or evidence upon physical or neurological examination of central nervous system (CNS) disease (e.g. seizures) unrelated to cancer unless adequately treated with standard medical therapy.
- 13. Active brain metastases or leptomeningeal metastases. Subjects with brain metastases are eligible if these have been treated and there is no magnetic resonance imaging (MRI except where contraindicated in which CT scan is acceptable) evidence of progression for at least 8 weeks after treatment is complete and within 28 days prior to first dose of study drug administration. Cases should be discussed with the medical monitor. There must also be no requirement for

- immunosuppressive doses of systemic corticosteroids (>10mg/day prednisone equivalents) for at least 2 weeks prior to study drug administration.
- 14. Surgical procedure (including open biopsy, surgical resection, wound revision, or any other major surgery involving entry into a body cavity) or significant traumatic injury within 28 days prior to start of study treatment, or anticipation of need for major surgical procedure during the course of the study.
- 15. Treatment with any chemotherapy, curative intent radiation therapy, biologics for cancer, or investigational therapy within 28 days of first administration of study treatment (subjects with prior cytotoxic or investigational products < 4 weeks prior to treatment might be eligible after discussion between investigator and sponsor, if toxicities from the prior treatment have been resolved to Grade 1 (NCI CTCAE version 4). Prior focal palliative radiotherapy must have been completed at least 2 weeks before study drug administration.
- 16. All toxicities attributed to prior anti-cancer therapy other than alopecia and fatigue must have resolved to Grade 1 (NCI CTCAE version 4) or baseline before administration of study drug. Subjects with toxicities attributed to prior anti-cancer therapy which are not expected to resolve and result in long lasting sequelae, such as neuropathy after platinum-based therapy, are permitted to enroll.
- 17. Known hypersensitivity to any of the study medications or Known hypersensitivity or allergy to Chinese hamster ovary cell products or any component of the NIVO formulation.
- 18. History of severe allergic, anaphylactic, or other hypersensitivity reactions to chimeric or humanized antibodies or fusion proteins.
- 19. History of autoimmune disease including but not limited to myasthenia gravis, myositis, autoimmune hepatitis, systemic lupus erythematosus, rheumatoid arthritis, inflammatory bowel disease, vascular thrombosis associated with antiphospholipid syndrome, Wegener's granulomatosis, Sjögren's syndrome, Guillain-Barré syndrome, multiple sclerosis, vasculitis, or glomerulonephritis (see Appendix IV for a more comprehensive list of autoimmune diseases).
 - a. Note: history of autoimmune-related hypothyroidism on a stable dose of thyroid replacement hormone may be eligible. Subjects with controlled type I diabetes mellitus on a stable insulin regimen, vitiligo or psoriasis not requiring systemic treatment may be eligible.
- 20. Prior allogeneic bone marrow transplantation or prior solid organ transplantation.
- 21. History of idiopathic pulmonary fibrosis (including pneumonitis), drug-induced pneumonitis, organizing pneumonia (i.e., bronchiolitis obliterans, cryptogenic organizing pneumonia), or evidence of active pneumonitis on Screening chest CT scan.
- 22. Treatment with systemic immunostimulatory agents (including but not limited to interferons or interleukin-2) within 4 weeks or five half-lives of the drug, whichever is shorter, prior to start of study treatment.
- 23. Treatment with systemic corticosteroids (>10 mg daily prednisone equivalents) or other systemic immunosuppressive medications (including but not limited to prednisone, dexamethasone, cyclophosphamide, azathioprine, methotrexate, thalidomide, and anti-tumor necrosis factor [TNF] agents) within 2 weeks prior to start of study treatment, or requirement for systemic immunosuppressive medications during the trial. The use of inhaled corticosteroids and mineralocorticoids (e.g., fludrocortisone) is allowed.
 - a. Note: Patients who have received acute, low-dose, systemic immunosuppressant medications (e.g., a one-time dose of dexamethasone for nausea) may be enrolled in the study after discussion with and approval by the Sponsor.
- 24. Positive test for human immunodeficiency virus (HIV).
- 25. Active hepatitis B (defined as having a positive hepatitis B surface antigen [HBsAg] test prior to randomization) or hepatitis C.

- a. Note: Patients with past hepatitis B virus (HBV) infection or resolved HBV infection (defined as having a negative HBsAg test and a positive antibody to hepatitis B core antigen antibody test) are eligible. Patients with detectable HBV-DNA are not eligible.
- b. Note: Patients positive for hepatitis C virus (HCV) antibody are eligible only if polymerase chain reaction testing is negative for HCV ribonucleic acid (RNA).
- 26. Active tuberculosis.
- 27. Administration of a live, attenuated vaccine within 4 weeks prior to start of study treatment or anticipation that such a live attenuated vaccine will be required during the study.
- 28. Prior treatment with CD137 agonists, anti-CTLA4, anti-PD-1, or anti-PD-L1 therapeutic antibody or drug specifically targeting T-cell co-stimulation or immune checkpoint pathways, including prior therapy with anti-tumor vaccines.
- 29. Pregnancy or lactation. A serum pregnancy test is required within 7 days prior to start of study treatment, or within 14 days with a confirmatory urine pregnancy test within 7 days prior start of study treatment.
- 30. For women who are not post-menopausal (< 12 months of non-therapy-induced amenorrhea) or surgically sterile (absence of ovaries and/or uterus): refusal to use a highly effective contraceptive method (i.e. with a failure rate of < 1% per year such as sexual abstinence, hormonal implants, combined oral contraceptives, vasectomized partner), during the study drug administration and for at least 6 months after the last dose of study medication. Periodic abstinence [e.g., calendar, ovulation, symptothermal, postovulation methods] and withdrawal are not acceptable methods of contraception. A combination of male condom with cap, diaphragm or sponge with spermicide (double barrier methods) is not considered a highly effective birth control method. Acceptable methods of contraception may include total abstinence in cases where the lifestyle of the patient ensures compliance. A vasectomized partner is a highly effective birth control method provided that partner is the sole sexual partner of the trial participant and that the vasectomized partner has received medical assessment of the surgical success.
- 31. For men: refusal to use a highly effective contraceptive method (i.e. with a failure rate of < 1 % per year such as vasectomy, sexual abstinence or female partner use of hormonal implants or combined oral contraceptives) during the study drug administration and for a period of at least 6 months after the last dose of study medication. Periodic abstinence [e.g., calendar, ovulation, symptothermal, post ovulation methods] and withdrawal are not acceptable methods of contraception. A combination of male condom with either, cap, diaphragm or sponge with spermicide (double barrier methods) is not considered highly effective, birth control methods. Acceptable methods of contraception may include total abstinence in cases where the lifestyle of the patient ensures compliance. A vasectomized trial participant is a highly effective birth control method provided that the trial participant has received medical assessment of the surgical success.

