7.14.1.1 General Plan to Manage Safety Concerns

7.14.1.1.1 Eligibility Criteria

Eligibility criteria were selected to guard the safety of patients in this trial. Results from the nonclinical toxicology studies and clinical data with TMZ, NIVO and IPI, as well as the nonclinical/clinical data from other checkpoint inhibitors, were taken into account. Specifically, patients at risk for study-emergent autoimmune conditions or with a prior diagnosis of autoimmune disease, patients with evidence of acute infections, and patients who have received a live-attenuated viral vaccine within 4 weeks before Day 1 are excluded from the study (see Section 4.2).

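### Exclusion criteria 4, 5 and 7 require every blood, liver or clotting limit to fail together, so one severely abnormal value passes the numeric limits

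*Protocol*

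**What the plan says.** Section 4.2 excludes a patient who meets any one of its numbered criteria. That *any* works between criteria. Inside three of them the connective is the opposite:

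- **Criterion 4 (blood):** "Inadequate hematological function indicated by all of the following", then WBC at or below 2, ANC below 1.5 and platelets below 100 (all x10^9/L), and haemoglobin below 9 g/dL. The haemoglobin line adds that "patients may have transfusions and/or growth factors to attain adequate Hb".
- **Criterion 5 (liver):** "Inadequate liver function indicated by all of the following", then bilirubin at or above 1.5 x ULN, transaminases at or above 3 x ULN (5 x with liver metastases), and ALP at or above 2 x ULN (5 x with liver metastases). The transaminase bullet opens "Aspartate transaminase (AST) and alanine aminotransferase (ALT", so both enzymes must be raised.
- **Criterion 7 (clotting, patients not on anticoagulants):** "INR > 1.5 and aPTT > 1.5 x ULN within 7 days prior to the start of study treatment".

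The Target Population part of the Protocol summary carries the same logic for all three. Section 4.1 contains no laboratory limits, so these are the only numeric entry limits for blood counts, liver tests and clotting. Criterion 6 (renal) has the same *all* header, but over a single bullet that already uses *or*, so it works.

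**The concern.** *All* is the right connective for an inclusion criterion that defines adequate function. In an exclusion criterion that defines inadequate function it reverses the rule, because the patient is kept out only if nothing is adequate. The wording may come from inclusion text turned into exclusions without changing the connective, but the protocol does not say so.

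These limits are the numeric entry check for about 100 patients who start temozolomide in the lead-in (section 4). For patients with malignant glioma on temozolomide, section 1.4.3.1 reports Grade 3 or 4 thrombocytopenia in 19% and neutropenia in 17%. Section 7 permits no waivers and requires adherence, so the written text is what sites are held to. Applied literally, it leaves a patient with very low platelets or high bilirubin to individual judgement at each of 10 centres instead of a common limit.

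**Working it through.** The protocol states no figure to reproduce here. The check is the AND/OR logic of each criterion.

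**Patterns.** With *k* limits there are 2^k − 1 patterns in which at least one limit fails. A joint (*all*) rule excludes only the one pattern in which every limit fails. An *any* rule excludes all of them.

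| Criterion | k | Patterns with at least one failure | Excluded as written | Pass | Excluded after fix |
|---|---|---|---|---|---|
| 4 (blood) | 4 | 2^4 − 1 = 15 | 1 | 14 | 15 |
| 5 (liver, three bullets) | 3 | 2^3 − 1 = 7 | 1 | 6 | 7 |
| 7 (clotting) | 2 | 2^2 − 1 = 3 | 1 | 2 | 3 |

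**Worked patients against the written limits.**

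- Platelets 40, WBC 5, ANC 3 (x10^9/L), Hb 12 g/dL: one of four limits fails, so criterion 4 is not met.
- WBC 2.1, ANC 0.5, platelets 30 (x10^9/L), Hb 7 g/dL: three of four fail, but WBC is not at or below 2, so criterion 4 is still not met.
- Bilirubin 4 x ULN with normal AST, ALT and ALP: one of three bullets fails, so criterion 5 is not met.
- INR 4 with normal aPTT, not anticoagulated: criterion 7 is not met.

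**Why the criterion 5 header alone is not enough.** Count AST and ALT separately, giving k = 4 and 15 patterns with a failure. As written, 1 is excluded. With only the header changed to *any*, the two patterns in which a single transaminase is the only failure still pass, so 15 − 2 = 13 are excluded. ALT 6 x ULN with AST 2.5 x ULN and no liver metastases is one of the two. With *or* between the enzymes as well, all 15 are excluded.

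**What the rest of the protocol shows about intent.**

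- The transfusion note in criterion 4 has a purpose only if low haemoglobin on its own can keep a patient out.
- Criterion 6 lets either renal limit exclude alone. No reason is given for treating the other organ systems differently.
- Section 7.14.1.1.1 states: "Eligibility criteria were selected to guard the safety of patients in this trial".
- Section 5.3.5 reduces temozolomide for ANC below 1.0 or platelets below 50 x10^9/L, each alone. Section 5.3.1 delays the checkpoint inhibitors for single liver abnormalities. These are on-treatment rules and bear on intent only. Still, a platelet count of 40 would call for a dose reduction on treatment while not meeting criterion 4 at entry.
- Section 8.9 counts ALT *or* AST, which supports that connective for the enzyme bullet only.

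**The case against.** The strongest reply is that other rules catch these patients. Criterion 10 excludes for a "laboratory finding giving reasonable suspicion of a disease or condition that contraindicates the use of any of the study medications", and it goes on to cover findings that raise the risk of treatment complications. Platelets of 40 or bilirubin of 4 x ULN could well fall under it, and it is an exclusion, not an option. Criterion 16 adds that "All toxicities attributed to prior anti-cancer therapy other than alopecia and fatigue must have resolved to Grade 1" or baseline. Criterion 15 asks for Grade 1 resolution when a patient enters early after cytotoxic or investigational treatment. Appendix I has haematology and chemistry checked within 48 hours before each administration.

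This narrows the consequence: such patients pass the numeric limits, not necessarily the whole of section 4.2. It does not repair the limits. Criterion 10 has no laboratory threshold, so centres may decide differently. Criterion 16 covers only abnormalities attributed to earlier cancer therapy, and so would not reach bilirubin raised by the disease itself. Criterion 15's condition applies only to early entry. The pre-dose checks in Appendix I set no entry limit.

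Other objections stand in part:

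- The pattern counts follow automatically from a joint rule and say nothing about how many patients are affected. The glioma rates are on-treatment rates.
- Evidence of intent is thinner for clotting than for blood and liver. Section 8.9 itself needs transaminase and bilirubin together, and section 5.3.1 requires no dose change for anaemia.
- If sites already read each limit as counting alone, practical harm is small. If they read the text literally, *any* tightens entry and could affect the planned yield of about 100 from about 400 screened. The protocol gives no screening laboratory data from which to estimate this.

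**Conclusion.** The concern holds. As written, criteria 4, 5 and 7 each exclude only the single pattern in which every limit fails (1 of 15, 1 of 7 and 1 of 3), so one severely abnormal value passes the numeric limits. The conclusion rests on the plain text of section 4.2 and the Synopsis, which agree with each other, and on the absence of any other numeric laboratory limit for entry. It assumes nothing about how often isolated abnormalities occur, and the share of patients affected cannot be derived from the protocol. Criteria 10, 15 and 16 soften the effect through judgement or in particular circumstances, without a fixed threshold. This is a safety rule that gives the wrong result when followed literally, so it needs correcting and should not be left to interpretation.

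**What to change.** Amend section 4.2 and the matching list in the Protocol summary, leaving every threshold as it is:

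1. Criteria 4 and 5: change *all* to *any* in the header.
2. Criterion 5, transaminase bullet: change *and* to *or* between AST and ALT.
3. Criterion 7: change *and* to *or* between the INR and aPTT limits. The Synopsis spells out both test names, so that edit has to be made to its own wording.
4. Criterion 6: change *all* to *any* for consistency only.

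The same amendment can tidy two related points that are not part of this eligibility gap. Section 7.7.1 defines childbearing potential in reverse; deleting the first *not* in that definition corrects it. Section 7.7.1 and footnote o of Appendix I allow a serum pregnancy test within 14 days without mentioning the confirmatory urine test within 7 days that criterion 29 then requires, so they should be aligned with criterion 29.

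The cost is a few words in two places, plus these two tidy-ups, by amendment. Sample size and analysis are unaffected. If any site has been applying the joint reading, its screening yield may fall.
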